3.0 Patient Eligibility

3.1 Inclusion Criteria

- 3.11 Diagnosis and previously untreated active multiple myeloma by IMWG diagnostic criteria for multiple myeloma
- 3.12 Age ≥ 18 years.
- 3.13 The following laboratory values obtained ≤ 14 days prior to registration.
- Calculated creatinine clearance (using Cockcroft-Gault equation below)* ≥ 30 mL/min
 - Absolute neutrophil count (ANC) $\geq 1000/\text{mm}^3$
 - Platelet count $\geq 75000/\text{mm}^3$
 - Hemoglobin ≥ 8.0 g/dL
 - Total bilirubin $\leq 1.5 \times \text{ULN}$
 - ALT and AST $\leq 3 \times \text{ULN}$

*Cockcroft-Gault Equation:

$$\text{Creatinine clearance for males} = \frac{(140 - \text{age})(\text{actual body weight in kg})}{(72)(\text{serum creatinine in mg/dL})}$$

$$\text{Creatinine clearance for females} = \frac{(140 - \text{age})(\text{actual body weight in kg})(0.85)}{(72)(\text{serum creatinine in mg/dL})}$$

- 3.14 Prior therapy for the treatment of solitary plasmacytoma is permitted, but >7 days should have elapsed from the last day of radiation.
NOTE: Prior therapy with clarithromycin, DHEA, anakinra, pamidronate or zoledronic acid is permitted. Any additional agents not listed must be approved by the Principal Investigator.
- 3.15 Measurable disease of multiple myeloma as defined by at least ONE of the following:
- Serum monoclonal protein ≥ 1.0 g/dL (see [Section 11.1](#) for definition)
 - >200 mg of monoclonal protein in the urine on 24 hour electrophoresis
 - Serum immunoglobulin free light chain ≥ 10 mg/dL AND abnormal serum immunoglobulin kappa to lambda free light chain ratio.
- 3.16 ECOG performance status (PS) 0 or 1 (See [Appendix I](#))
- 3.17 Provide written informed consent.
- 3.18 Negative pregnancy test done ≤ 7 days prior to registration, for women of childbearing potential only.
- 3.19a Willing to follow strict birth control measures as suggested by the study.
- 3.19a1 Female patients: If they are of childbearing potential, must agree to one of the following:
- Practice 2 effective methods of contraception, at the same time, from the time of signing the informed consent form through 90 days after the last dose of study drug, AND must also adhere to the guidelines of any treatment-specific pregnancy prevention program, if applicable, OR

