- Agree to practice true abstinence when this is in line with the preferred and usual lifestyle of the subject. (Periodic abstinence [eg, calendar, ovulation, symptothermal, post-ovulation methods] and withdrawal are not acceptable methods of contraception.)
- 3.19a2 Male patients: even if surgically sterilized (i.e., status post-vasectomy), must agree to one of the following:
- Agree to practice effective barrier contraception during the entire study treatment period and through 120 days after the last dose of study drug, OR
 - Must also adhere to the guidelines of any treatment-specific pregnancy prevention program, if applicable, OR
 - Agree to practice true abstinence when this is in line with the preferred and usual lifestyle of the subject. (Periodic abstinence (eg, calendar, ovulation, symptothermal, post-ovulation methods] and withdrawal are not acceptable methods of contraception.)
- 3.19b Willing to return to enrolling institution for follow-up (during the Active Monitoring Phase of the study).
- 3.19c Willing to provide consent to IRB#521-93 and provide research tissue and blood specimens.
- 3.2 Exclusion Criteria
- 3.21 MGUS or smoldering myeloma.
- 3.22 Prior cytotoxic chemotherapy or corticosteroids for the treatment of multiple myeloma.
NOTE: Prior corticosteroid use for the treatment of non-malignant disorders is permitted
- 3.23 Diagnosed or treated for another malignancy ≤ 2 years before study enrollment or previously diagnosed with another malignancy and have any evidence of residual disease.
NOTE: Patients with nonmelanoma skin cancer or carcinoma in situ of any type are not excluded if they have undergone complete resection.
- 3.24 Any of the following because this study involves an investigational agent whose genotoxic, mutagenic and teratogenic effects on the developing fetus and newborn are unknown:
- Pregnant women
 - Nursing women
 - Men or women of childbearing potential who are unwilling to employ adequate contraception
- 3.25 Other co-morbidity which would interfere with patient's ability to participate in trial, e.g. uncontrolled infection, uncompensated heart or lung disease.
- 3.26 Other concurrent chemotherapy or any ancillary therapy considered investigational.
NOTE: Bisphosphonates are considered to be supportive care rather than therapy, and are thus allowed while on protocol treatment.
- 3.27 Peripheral neuropathy \geq Grade 3 on clinical examination or Grade 2 with pain during the screening period.

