- 3.28 Major surgery ≤ 14 days prior to study registration.
- 3.29a Radiotherapy ≤ 14 days prior to registration.
NOTE: If the involved field is small, 7 days will be considered a sufficient interval between treatment and administration of study drugs
- 3.29b Participation in any other clinical trials with other investigational agents not included in this trial, ≤ 21 days prior to registration
- 3.29c Active autoimmune disease that has required systemic treatment in the past 2 years (i.e. with use of disease modifying agents, corticosteroids or immunosuppressive drugs).
NOTE: Replacement therapy (eg., thyroxine, insulin, or physiologic corticosteroid replacement therapy for adrenal or pituitary insufficiency, etc.) is not considered a form of systemic treatment.
- 3.29d Has a history of (non-infectious) pneumonitis that required steroids or current pneumonitis.
- 3.29e Active infection requiring systemic therapy.
- 3.29f History or current evidence of any condition, therapy, or laboratory abnormality that might confound the results of the trial, interfere with the subject's participation for the full duration of the trial, or is not in the best interest of the subject to participate, in the opinion of the treating investigator.
- 3.29g Known psychiatric or substance abuse disorders that would interfere with cooperation with the requirements of the trial.
- 3.29h Is pregnant or breastfeeding, or expecting to conceive or father children within the projected duration of the trial, starting with the pre-screening or screening visit through 120 days after the last dose of trial treatment.
- 3.29i Received prior therapy with an anti-PD-1, anti-PD-L1, or anti-PD-L2 agent.
- 3.29j Known history of Human Immunodeficiency Virus (HIV) (HIV 1/2 antibodies).
- 3.29k Known active Hepatitis B (e.g., HBsAg reactive) or Hepatitis C (e.g., HCV RNA [qualitative] is detected).
- 3.29l Received a live vaccine ≤ 30 days of planned start of study therapy.

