- c) Excretion – The systemic clearance of pembrolizumab is ~0.22 L/day and the terminal elimination half-life ($t_{1/2}$) is estimated to be ~26 days.
- d) Metabolism - Pembrolizumab is catabolized by general protein degradation processes; typical small molecule metabolic pathways (eg, cytochrome P450 enzymes, glucuronosyltransferases) do not contribute to its clearance.

15.16 **Potential Drug Interactions:** There are no known significant drug interactions.

15.17 **Known potential toxicities:**

Common known potential toxicities, > 10%:

Dermatologic: Pruritus, skin rash
 Gastrointestinal: diarrhea
 Neuromuscular & skeletal: arthralgia, back pain
 Respiratory: Cough

Less common known potential toxicities, 1% - 10%:

Infusion related reactions
 Dermatologic: vitiligo, severe skin reactions
 Endocrine & metabolic: Hypothyroidism, hyperthyroidism, hyponatremia
 Gastrointestinal: Colitis, abdominal pain
 Respiratory: Pneumonitis

Rare known potential toxicities, <1% (Limited to important or life-threatening):

Secondary adrenocortical insufficiency (immune-mediated), hepatitis (including autoimmune hepatitis), hypophysitis, nephritis, Guillain-Barre syndrome (immune-mediated), myositis (immune-mediated), pancreatitis (immune-mediated), uveitis (immune-mediated), and Type 1 diabetes mellitus.

Stevens-Johnson syndrome, Toxic Epidermal Necrolysis, and Immune-mediated myocarditis

Two important potential risks have been identified, although the data available thus far for these events does not provide sufficient evidence of a causal relationship to pembrolizumab. The two important potential risks are: a) myasthenic syndrome, and b) an increased risk of severe complications (such as early severe graft versus host disease and venoocclusive disease) of allogeneic transplant in patients with hematologic malignancies who have previously been treated with PD-1 inhibitors. The Sponsor continues to monitor and collect data on these potential risks in order to further characterize their potential relationship to Pembrolizumab.

15.18 **Drug procurement:** Pembrolizumab will be provided free of charge to study participants by Merck.

15.19 **Nursing Guidelines:**

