single 25-mg dose warfarin had no effect on the pharmacokinetics of lenalidomide. However, it is not known whether there is an interaction during clinical use.

Concomitant administration with lenalidomide 10 mg/day increased the plasma exposure of digoxin (0.5 mg, single dose) by 14%. It is not known whether the effect will be different in the therapeutic situation (higher lenalidomide doses and concomitant treatment with dexamethasone).

15.27 **Known potential toxicities:**

Pregnancy Warning: Lenalidomide is structurally related to thalidomide, a known human teratogen. Therefore, in an effort to prevent to the greatest extent possible any chance of fetal exposure, lenalidomide is available through a controlled distribution program, specifically a pregnancy prevention program called Revlimid REMS. It is contraindicated in women who are or may become pregnant. Female subjects of childbearing potential are required to submit to regular pregnancy testing, and to agree to use effective forms of birth control as outlined in study protocols. Male subjects, even those who have had a vasectomy, must agree to use a condom during sexual contact with a pregnant woman or a woman who can become pregnant.

Very Common AEs (≥10%): anemia, febrile neutropenia, leukopenia, neutropenia, thrombocytopenia, cataracts, blurred vision, abdominal pain, constipation, diarrhea, dyspepsia, nausea, vomiting, asthenia, chills, edema including peripheral, fatigue, pyrexia, abnormal liver function tests, bacterial, viral and fungal infections (including opportunistic infections), bronchitis, nasopharyngitis, sinusitis, pneumonia, rhinitis, upper respiratory tract infection, urinary tract infection weight decreased, decreased appetite, hyperglycemia, hypocalcemia, hypokalemia, arthralgia, back pain, bone pain, muscle spasms, musculoskeletal pain, myalgia, pain in extremity, dizziness, dysgeusia, headache, hypoesthesia, neuropathy peripheral, neuropathy, tremor, depression, insomnia, renal failure, cough, dyspnea, epistaxis, pharyngitis, pulmonary embolism, dry skin, pruritus, rash, and deep vein thrombosis.

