Drug will be shipped directly to the patient through Revlimid REMS Program. Any unused lenalidomide should be returned for disposition in accordance with the REVLIMID REMS™ program.

15.29 **Nursing Guidelines**

15.291 The most common side effects are neutropenia and thrombocytopenia.

15.292 Due to the highly teratogenic potential of the closely related thalidomide, it is highly recommended that all women of childbearing age group and all men use effective contraception during therapy. All staff who are pregnant or who can become pregnant should not handle this drug outside of its original packaging.

15.293 Instruct patient to report any rash immediately to the study team.

15.294 Lenalidomide capsules should be swallowed whole, and should not be broken, chewed or opened.

15.295 If a dose of lenalidomide is missed, it should be taken as soon as possible on the same day. If it is missed for the entire day, it should not be made up.

15.296 Patients who take more than the prescribed dose of lenalidomide should be instructed to seek emergency medical care if needed and contact study staff immediately.

15.3 **Dexamethasone for Oral Administration (DXM)**

15.31 **Background:** Dexamethasone is an adrenal corticosteroid compound. Dexamethasone decreases inflammation by suppression of neutrophil migration, decreased production of inflammatory mediators, and reversal of increased capillary permeability; suppresses normal immune response. Dexamethasone's mechanism of antiemetic activity is unknown.

15.32 **Formulation:** Commercially available for oral administration as:
Tablets [scored]: 0.5 mg, 0.75 mg, 1 mg, 1.5 mg, 2 mg, 4 mg, and 6 mg.

Solution, oral: 0.5 mg/mL (500 mL).

Solution, oral concentrate: Dexamethasone Intensol: 1 mg/mL (30 mL).

- 15.33 **Preparation, storage, and stability:** Refer to package insert for complete preparation and dispensing instructions. Store oral tablets at room temperature between 20°C to 25°C (60°F to 77°F). Protect from moisture. Dispense in a well-closed, light-resistant container as defined in the USP/NF. Store oral liquid at room temperature, do not freeze. Do not use if solution contains a precipitate. Refer to commercial package for drug expiration date.
- 15.34 **Administration:** Refer to the treatment section for specific administration instructions. May be taken with meals to decrease GI upset.
- 15.35 **Pharmacokinetic information:**
Onset of action: Prompt
Duration of metabolic effect: 72 hours

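### Two-method contraception for women may stop at 90 days (3.19a1), 30 days before the 120-day no-conception period in 3.29h ends, and no reason is given

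*Combined protocol and SAP*

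**What the plan says.** Section 3.19a1 gives women of childbearing potential two options. The first is two effective contraceptive methods at the same time, "from the time of signing the informed consent form through 90 days after the last dose of study drug", together with a second condition: "AND must also adhere to the guidelines of any treatment-specific pregnancy prevention program", where one applies. The second is true abstinence, with no end date.

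Section 3.29h excludes anyone who is pregnant, is breastfeeding, or expects to conceive or father a child during a period "starting with the pre-screening or screening visit through 120 days after the last dose of trial treatment". It names conceiving as well as fathering, so it applies to women.

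For men, the first option in 3.19a2 is "effective barrier contraception during the entire study treatment period and through 120 days after the last dose of study drug, OR". It is one of three alternatives, so it is a reference point and not a duty on every man.

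Section 10.52 has pregnancies reported if they occur within 120 days of completing the trial, or within 30 days of stopping treatment if new anticancer therapy starts, whichever is earlier.

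**The concern.** The protocol uses 120 days for the no-conception period, for the men's barrier option and for the main pregnancy-reporting window. The women's two-method period is the only one of the contraception and conception periods that is shorter, and no reason is given.

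Section 3.29h screens out planned conception at entry. What it cannot prevent is an unplanned conception, or a change of plan, after treatment has ended. Contraception is the safeguard against that, and for a woman who follows the two-method option exactly it may lapse 30 days before the 3.29h period ends. Section 3.24 describes the investigational agent as one whose "genotoxic, mutagenic and teratogenic effects on the developing fetus and newborn are unknown". Staff reading 3.19a1 and staff reading 3.29h could also advise the same woman differently.

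**Working it through.** **Same starting point.** Section 3.19a1 counts from the last dose of study drug and 3.29h from the last dose of trial treatment. Sections 19.1 and 19.2 call all three agents study drugs, so both read as the same date.

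**Length of the gap.** 120 − 90 = 30 days, and 30/120 = 25% of the longer period.

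**Does other text set a contraception duty for women over days 91 to 120?**

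| Section | What it covers | Fills days 91–120? |
|---|---|---|
| 3.24 | Excludes those unwilling to use adequate contraception | No end date given |
| 3.19a1, prevention program | Adherence to any treatment-specific program | No post-dose duration given |
| 15.27 (lenalidomide) | Women are required "to agree to use effective forms of birth control as outlined in study protocols" | Refers back to the protocol, where the only post-dose figure for women is 90 days |
| 15.292 (lenalidomide) | Recommends that "all women of childbearing age group and all men use effective contraception during therapy" | On-treatment period only |
| 3.29h | Expectation of conceiving, judged at entry | Sets no later duty |
| 10.52 | Reporting and follow-up of pregnancies | Not prevention |

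The 90 days in 3.19a1 is therefore the only post-dose contraception period stated for women.

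**Scale in drug exposure.** Section 15.15 says the terminal half-life of pembrolizumab "is estimated to be ~26 days". With first-order decline, and pembrolizumab given up to the last dose, the fraction of the end-of-treatment level remaining after t days is 0.5^(t/h), where h is the half-life.

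- Day 90: 90/26 = 3.46 half-lives; 0.5^3.46 = 9.1%.
- Day 120: 120/26 = 4.62 half-lives; 0.5^4.62 = 4.1%.

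The documents give no range for the half-life. Assuming 22 to 30 days:

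| Half-life (days) | Remaining at day 90 | Remaining at day 120 |
|---|---|---|
| 22 (assumed) | 5.9% | 2.3% |
| 26 (15.15) | 9.1% | 4.1% |
| 30 (assumed) | 12.5% | 6.25% |

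**Scale in patients.** Section 16.63 expects 14 women among 41 patients, and 1.1 gives a median age at onset of 65 to 70 years. The number of childbearing potential is not stated; 0 to 3 is an assumption.

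**The case against.** The strongest reply is that the two clauses do not strictly contradict each other. One sets a contraception duty; the other is an entry criterion about intention. A woman can satisfy both by using two methods to day 90 and having no plan to conceive before day 120. That is right as far as it goes: the mismatch is between two periods for the same risk, not between two identical requirements. It does not explain why the safeguard against unplanned conception ends first.

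The lenalidomide prevention program and the consent pages might set a longer period. Neither the program's post-dose rules nor the consent text is available, so what women are actually told is unknown. The point is limited to the protocol's wording.

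Section 10.52 means that a pregnancy in the window may still be reported and followed. That softens the consequence, but it is not prevention, and it uses 120 days again.

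The drug-level figures assume that pembrolizumab continued to the last dose. Section 8.1 lets it be stopped while the other drugs continue, and then less would remain.

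Finally, the documents justify neither 90 nor 120 days. Agreement among clauses supports a single period; it does not prove that 120 is the right one. This stands, and it is why a justified 90 days would also resolve the point.

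**Conclusion.** The inconsistency holds, at minor severity. The two-method option lets contraception stop 30 days before the 3.29h period ends, and no explanation is given. The finding does not extend to the abstinence option, which has no end date. The residual pembrolizumab figures rest on the 26-day half-life, first-order decline and dosing to the last day. With no safe level in the documents, they do not show that 90 days is harmful or that 120 days is safe. Few patients are likely to be affected. The primary endpoint, sample size and error rates do not change.

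**What to change.** In 3.19a1, change 90 to 120 days after the last dose. That brings the gap with 3.29h to zero and matches the men's barrier option in 3.19a2. Carry the same period into the patient information. If 90 days is intended for women, state the reason in 3.19a1 and align 3.29h.

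The text change is one number plus the matching patient information. Amendments need IRB approval before they take effect (6.2). There is no added visit or test, and no effect on sample size or timelines.

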4.0 Test Schedule

4.1 Schedule of assessments

Tests and Procedures	Screening		Active Treatment ¹						
	≤30 days	≤14 days	Cycles 1-3 to be repeated beyond 3 cycles						
			Cycle 1		Cycle 2		Cycle 3		End of Induction treatment
			Weekly (For first 2 cycles)	Cycle 1, Day 1, Pre-treatment ¹⁰	Pembrolizumab infusion Cycle 1, Day 22, Pre-treatment ¹¹	Cycle 2, Day 1, Pre-treatment	Pembrolizumab infusion Cycle 2, Day 15, Pre-treatment ¹¹	Cycle 3, Day 1, Pre-treatment	
Complete medical history	X								
Adverse Event monitoring		X		X		X		X	X
Physical exam, including weight, vital signs		X		X		X		X	X
Height		X							
Performance status (ECOG scale)		X		X		X		X	X
CBC with diff (includes hemoglobin, ANC, WBC with complete differential, platelets)		X	X	X	X	X	X	X	X
Prothrombin time (PT)	X								
Chemistry group to include sodium, potassium, glucose, alkaline phosphatase; Total and Direct bilirubin; SGOT (AST); SGPT (ALT); serum creatinine, calcium		X	X	X	X	X	X	X	X
LDH, Beta ₂ -microglobulin, Plasma cell assessment	X								
sTSH	X			Every 6 months while on treatment					
Electrophoresis of serum and urine (SPEP/UPEP)		X		X ⁹		X ⁹		X ⁹	X ⁹
Affected Immunoglobulin ²		X		X		X		X	X
Immunofixation serum and urine	X			X ³		X ³		X ³	X ³
Immunoglobulin free light chain		X		X ⁴		X ⁴		X ⁴	X ⁴
X-ray skeletal survey or low dose whole body CT	X								
Bone marrow aspirate and biopsy, myeloma FISH, plasma cell proliferation, and flow cytometry	X			X ⁵		X ⁵		X ⁵	X ⁵

	Screening		Active Treatment ¹							
	≤30 days	≤14 days	Cycles 1-3 to be repeated beyond 3 cycles							
			Cycle 1		Cycle 2		Cycle 3		End of Induction treatment	
			Weekly (For first 2 cycles)	Cycle 1, Day 1, Pre-treatment ¹⁰	Pembrolizumab infusion Cycle 1, Day 22, Pre-treatment ¹¹	Cycle 2, Day 1, Pre-treatment	Pembrolizumab infusion Cycle 2, Day 15, Pre-treatment ¹¹	Cycle 3, Day 1, Pre-treatment		Pembrolizumab infusion Cycle 3, Day 8, Pre-treatment ¹¹
Tests and Procedures										
Research bone marrow ^R (IRB 521-93)	X			X ⁵		X ⁵		X ⁵		X ⁵
Research blood sample ^R (IRB 521-93)	X			X ⁶		X ⁶		X ⁶		
Chest x-ray	X									
Serum pregnancy test		X ⁷								
Patient Medication Diary (Appendix II) ⁸ .				X		X		X		X

Cycle length during induction = 28 days

- 1) All scheduled visits will have a window of ± 4 days, except pembrolizumab infusion days which will have a window of ± 1 day
- 2) Affected immunoglobulin refers to the baseline M-protein type, that is, IgG, IgA, or IgD. Not applicable if patient “non-secretory” or if patient has no heavy chain, i.e. light chain myeloma.
- 3) Immunofixation (IF) needed only in the absence of M-spike to document CR or sCR.
- 4) FLC is required only if used to assess disease response during active phase
- 5) At the end of 4 cycles and to document CR at any time point.
- 6) End of each cycle for first 4 cycles, and then at time of disease progression.
- 7) For women of childbearing potential only. Must be done ≤ 7 days prior to registration
- 8) The diary must begin the day the patient starts taking the medication and must be completed per protocol and returned to the treating institution.
- 9) Urine Electrophoresis required after baseline only if used to assess disease response
- 10) Does not need to be repeated at Cycle 1 Day 1. Baseline values can be used for Cycle 1.
- 11) If pembrolizumab is discontinued, the patient may continue treatment with the remaining drugs and these visits do not apply.
- R) Research funded (see Section 19.0). Will be charged to study and not to patient’s account.

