7.4 Stem cell collection and transplant

Patients are allowed to collect stem cells and proceed to transplant any time after 4 cycles of initial therapy. If patient goes to transplant, they will go directly to event monitoring per Section 4.2 and the transplant should be reported on the event monitoring form. In the case that patients are unable to go to transplant due to other reasons, they can continue on study. In those cases, therapy may be interrupted for up to 4 weeks for the purpose of stem cell collection. Stem cells can be collected using standard institutional protocols. Any delay beyond 4 weeks should be discussed with the study PI prior to reinitiating protocol therapy.

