9.8 Diarrhea/Colitis

Subjects should be carefully monitored for signs and symptoms of enterocolitis (such as diarrhea, abdominal pain, blood or mucus in stool, with or without fever) and of bowel perforation (such as peritoneal signs and ileus).

- All subjects who experience diarrhea/colitis should be advised to drink liberal **quantities of clear fluids. If sufficient oral fluid intake is not feasible, fluid and**

electrolytes should be substituted via IV infusion. For Grade 2 or higher diarrhea, consider GI consultation and endoscopy to confirm or rule out colitis.

- For **Grade 2 diarrhea/colitis** that persists greater than 3 days, administer oral corticosteroids.
- For **Grade 3 or 4 diarrhea/colitis** that persists > 1 week, treat with intravenous steroids followed by high dose oral steroids.
- When symptoms improve to Grade 1 or less, steroid taper should be started and continued over no less than 4 weeks.

9.9a Type 1 diabetes mellitus

If new onset, including diabetic ketoacidosis [DKA] or \geq Grade 3 Hyperglycemia, if associated with ketosis (ketonuria) or metabolic acidosis (DKA)

- For **T1DM** or **Grade 3-4** Hyperglycemia
- Insulin replacement therapy is recommended for Type I diabetes mellitus and for Grade 3-4 hyperglycemia associated with metabolic acidosis or ketonuria.
- Evaluate patients with serum glucose and a metabolic panel, urine ketones, glycosylated hemoglobin, and C-peptide.

9.9b Hypophysitis:

- For **Grade 2** events, treat with corticosteroids. When symptoms improve to Grade 1 or less, steroid taper should be started and continued over no less than 4 weeks. Replacement of appropriate hormones may be required as the steroid dose is tapered.
- For **Grade 3-4** events, treat with an initial dose of IV corticosteroids followed by oral corticosteroids. When symptoms improve to Grade 1 or less, steroid taper should be started and continued over no less than 4 weeks. Replacement of appropriate hormones may be required as the steroid dose is tapered.

9.9c Hyperthyroidism or Hypothyroidism:

Thyroid disorders can occur at any time during treatment. Monitor patients for changes in thyroid function (at the start of treatment, periodically during treatment, and as indicated based on clinical evaluation) and for clinical signs and symptoms of thyroid disorders.

- **Grade 2** hyperthyroidism events (and **Grade 2-4** hypothyroidism):

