- 15.191 Pembrolizumab side effects vary greatly from those of traditional chemotherapy and can vary in severity from mild to life threatening. Instruct patients to report any side effects to the study team immediately. Side effects may be immediate or delayed up to months after discontinuation of therapy. Most side effects are reversible with prompt intervention of corticosteroids.
- 15.192 Diarrhea can be seen however is less common than that seen with anti-CTLA-4 agents. However it can be severe, leading to colonic perforation. Instruct patients to report ANY increase in the number of stools and/or change in baseline, blood in the stool, abdominal pain to the study team immediately.
- 15.193 Rash/pruiritis/dermatitis is seen. Patients should report any rash to the study team. Treat per [Section 9.0](#) and monitor for effectiveness.

- 15.194 Monitor LFT's closely as elevations in these levels could indicate early onset autoimmune hepatitis. Patients should also be instructed to report any jaundice, or right upper quadrant pain to the study team immediately.
 - 15.195 Pneumonitis can be seen and may be mild (only seen on imaging) to severe. Patients should be instructed to report any SOB, dyspnea, cough, chest pain, etc. to the study team immediately. Patients reporting these symptoms should have a pulse ox checked and consider immediate imaging per the treating MD.
 - 15.196 Endocrinopathies (including hypopituitarism, hypothyroidism, hypophysitis, and adrenal insufficiency) are seen with this agent. Patients may present only with the vague sense of fatigue and "not feeling well". Additional symptoms may be that of nausea, sweating and decreased activity tolerance. Instruct patients to report these signs or symptoms immediately and obtain appropriate labs as ordered by MD.
 - 15.197 Patients who are started on steroid therapy for any side effects of pembrolizumab toxicity should be instructed to take the steroids as ordered, and not to discontinue abruptly as symptoms may return and be severe. Patients may be on steroid therapy for weeks. Instruct patients to report any increase or change in side effects with any dosage decrease as patients may need a slower taper.
 - 15.198 Fatigue is common and may or may not be associated with immune related side effects. Assess patient's fatigue level prior to each cycle of therapy and report any *changes to the study team*.

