16.3 Analysis Plan

16.31 Primary Outcome Analyses:

- 16.311 Definition: The primary endpoint in the phase II portion of this trial is the proportion of complete plus very good partial responses after 4 cycles of induction treatment. A success is defined as an sCR, CR, or VGPR noted as the objective status on two consecutive evaluations. Response will be evaluated using the first 4 cycles of induction therapy. All patients meeting the eligibility criteria who have signed a consent form and have begun treatment will be evaluable for response, with the exception of patients who are determined to be a major violation.
- 16.312 Estimation: The proportion of successes will be estimated by the number of successes divided by the total number of evaluable patients.

Confidence intervals for the true success proportion will be calculated according to the approach of Duffy and Santner (Duffy D 1987).

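### A patient who leaves treatment before about 6 months has no scheduled on-treatment thyroid test, so the thyroid event rate may be under-ascertained

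*Combined protocol and SAP*

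**What the plan says.** The sTSH row of the Section 4.1 schedule has one mark in the 30-day screening column and then "Every 6 months while on treatment". No cycle column carries its own sTSH mark, and neither does End of Induction, where blood count and chemistry are both marked. The same section gives "Cycle length during induction = 28 days" and "All scheduled visits will have a window of ± 4 days" (one day for infusion visits).

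Section 9.9c warns that thyroid disorders may arise at any point in treatment and instructs: "Monitor patients for changes in thyroid function (at the start of treatment, periodically during treatment, and as indicated based on clinical evaluation". It gives no interval.

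There are two planned ways off treatment before six months:

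- Section 7.4: "Patients are allowed to collect stem cells and proceed to transplant any time after 4 cycles of initial therapy". It continues: "If patient goes to transplant, they will go directly to event monitoring per Section 4.2". The Section 4.2 table lists no laboratory tests.
- Section 7.2 sends patients to event monitoring for insufficient response, judged after 2 and 4 cycles.

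Goal 2.24 is to determine the toxicities of the regimen. Section 16.325 treats every eligible patient who starts treatment as evaluable for adverse events and tabulates the maximum grade of each event type.

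**The concern.** A rate needs a numerator and a denominator observed on the same footing. Here a patient treated for four cycles counts fully in the adverse-event denominator but has no scheduled chance of a thyroid abnormality being detected by a test after baseline. A patient treated for eight cycles has one. The trial enrolls transplant-eligible patients and opens transplant after Cycle 4, so early departure is a planned route.

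Testing prompted by symptoms replaces the scheduled test only in part. Of endocrine toxicity, Section 15.196 says: "Patients may present only with the vague sense of fatigue". Section 15.198 calls fatigue common with pembrolizumab, and Section 15.27 lists fatigue and asthenia among the very common effects of lenalidomide. Section 10.8 solicits fatigue at each evaluation but no thyroid term. A thyroid event could therefore be recorded as fatigue from the regimen. At stake is the completeness of one part of a secondary safety objective.

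**Working it through.** **Inputs.** Cycle length 28 days, visit window 4 days, screening window 30 days (4.1). Pembrolizumab every 21 days (7.1). Treatment starts at most 14 days after registration (6.17). A new cycle may be delayed by at most 4 weeks (8.11). Assumption: six months = 182.6 days, counted from Cycle 1 Day 1, because the plan gives no anchor.

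**1. Reproduce the plan's calendar.** Infusions fall on day 1 + 21k. Days 22, 43 and 64 map to Cycle 1 Day 22, Cycle 2 Day 15 and Cycle 3 Day 8, exactly as the column heads in 4.1 show.

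**2. End of the first four cycles.** 4 × 28 = day 112, or day 116 with the window. Section 16.311 uses the same period for the primary endpoint: "Response will be evaluated using the first 4 cycles of induction therapy".

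**3. First scheduled on-treatment sTSH.** 182.6 / 28 = 6.5 cycles, so about day 183. Cycle 7 runs from day 169 to day 196. The test falls about 183 − 112 = 71 days after the end of Cycle 4.

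**4. Infusions before that test.** By day 112 there are six (days 1, 22, 43, 64, 85, 106). By day 183 there are nine (adding days 127, 148, 169).

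**5. Who has no scheduled on-treatment value.** Planned cycle ends are Cycle 2 = day 56, Cycle 4 = day 112, Cycle 5 = day 140, Cycle 6 = day 168. All precede day 183. With the windows working against the claim, 168 + 4 = 172 is still before 182.6 − 4 = 178.6.

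**6. Sensitivity to the anchor.** Suppose the six months ran from the earliest possible screening test, 30 + 14 = 44 days before Day 1. The next test is then due on day 182.6 − 44 = 138.6, or 134.6 with the window. That is still after day 112 (and day 116). A patient leaving at the end of Cycle 5 (day 140) could then have a value, so the affected group shrinks to those leaving before about day 139.

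**7. Sensitivity to delays.** Two maximum delays put the end of Cycle 4 at 112 + 2 × 28 = day 168, still before day 183. Three put it at 112 + 3 × 28 = day 196, after it. Only repeated long delays bring a scheduled value inside four cycles.

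**8. Can the shortfall be sized?** Missed events = patients × thyroid event rate × share of events arising in patients who leave early × share of those events never tested for. Section 15.17 places hypothyroidism and hyperthyroidism in the 1% to 10% group. With 37 evaluable patients that is 0.37 to 3.7 expected events of each type; with the maximum accrual of 41 it is 0.41 to 4.1. These figures count all expected events, not missed ones. The documents give neither of the last two factors, so the shortfall could lie anywhere from zero up to those totals.

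**The case against.** The strongest reply is that the protocol does not leave detection to chance. Section 10.56 has patients assessed before each dose for possible events of clinical interest, with further testing when something suggests an immune-related cause. Section 15.196 tells patients to report endocrine symptoms at once and has laboratory tests ordered. Fatigue is graded at every evaluation, and examination and vital signs are scheduled each cycle. This stands: clinically apparent events have a route to diagnosis, and examination as well as symptoms can prompt a test. It does not give early leavers a scheduled test.

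Three stronger readings are tempting, and the documents do not support them:

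- **That 4.1 contradicts 9.9c.** Section 9.9c names no interval. The screening test covers the start of treatment, six-monthly testing is periodic, and unscheduled tests are allowed. The gap is only that the periodic element does not reach patients treated for less than six months.
- **That transplant patients never have an on-treatment value.** Section 7.4 sets no latest date for transplant. A patient who leaves after about day 183 has had a test scheduled.
- **That the lenalidomide action in 8.3 is missed.** It applies from Grade 2. The protocol does not reproduce the thyroid grade definitions, so it cannot be shown from the documents that a silent abnormality would reach that grade.

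It is also fair to say that four cycles is the response window, not a window set for toxicity. The relevant boundary for adverse events is the time of leaving treatment.

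**Conclusion.** The point holds in limited form. On the planned calendar no scheduled on-treatment sTSH falls by day 112, and patients leaving before about six months have none. For them thyroid events are ascertained by clinical prompting alone, while 16.325 keeps them in the denominator. The thyroid rate under goal 2.24 may therefore be biased downward, more so among early leavers, by an amount that cannot be calculated from the documents.

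The primary endpoint and the interim rule do not use sTSH. The adverse event stopping rule counts only related non-hematologic events of Grade 4 or higher. I assume that a thyroid event of that severity would come to notice without a scheduled test.

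The conclusion assumes that six months runs from about Cycle 1 Day 1 (step 6 shows the effect of an earlier anchor), that delays are not repeated and long, and that the schedule table was read correctly from the PDF. Section 10.56 refers to an Appendix 4 guidance document that is not in the supplied text; any thyroid testing it requires would narrow or close the gap.

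**What to change.** Reconcile the sTSH row of 4.1 with 9.9c so that patients who leave before six months also have a scheduled post-baseline value. One option is to use the blood already drawn at the End of Induction visit. That visit has no fixed day in 4.1, so state whether it applies to patients who stop after Cycle 2 or leave for transplant. State also the date from which the six months are counted. The clinical team sets the test timing and should take the Appendix 4 guidance into account.

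The cost is about one additional assay per patient and one cell in the schedule.

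If the schedule stays as it is, say in the adverse event analysis and the report that thyroid events before six months were clinically ascertained only, and give the number of patients with no post-baseline sTSH beside the rate. That costs one sentence and one count.
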